12 TREATMENTS

12.1 Details of Study Medication

12.1.1 Investigational Products Administered

“Study drug” or “study medication” refers to nemolizumab or placebo drug product for purposes of this double-blind study. The list of excipients is detailed in the IB.

The Sponsor has developed a lyophilized powder in a DCS which holds the lyophilized nemolizumab or placebo, and the sterile water for injection separately.

Subjects will receive a loading dose of nemolizumab (60 mg) or placebo by two SC injections at baseline (30 mg + 30 mg, placebo + placebo), and a 30 mg or 60 mg dose of nemolizumab or placebo by two SC injections (30 mg + placebo, 30 mg + 30 mg, placebo + placebo) at Weeks 4 and 8. All the study drug treatment should be performed within four hours following the completion of the hemodialysis .

12.1.2 Identity of Investigational Products

Table 2 Description and Usage of Investigational Products

	Investigational Product	Placebo
Name (internal code)	Nemolizumab (CD14152)	CD14152 placebo (N/A)
Pharmaceutical form	Lyophilized powder for solution for injection in a DCS	Lyophilized powder for solution for injection in a DCS
Dosage	30 mg (with a loading dose of 60 mg at baseline) or 60 mg	N/A
Dose regimen	Q4W	Q4W
Route ^a	SC use by subjects or clinic staff after reconstitution	SC use by subjects or clinic staff after reconstitution
Duration of treatment	12 weeks: baseline to Week 12	12 weeks: baseline to Week 12

Abbreviations: DCS = dual-chamber, single-use syringe; N/A = not applicable; Q4W = every four weeks.

^a All injections are performed at the study center. Injections by subjects are performed under supervision by clinic staff, after appropriate training.

12.1.3 Preparation

A pharmacist (or other qualified personnel) will prepare study medication for injection according to instructions provided in the current version of the pharmacy manual and the Instructions for Use. Study medication preparation should be conducted in a secured and clean area with limited access to only designated personnel at the time of the preparation. Good hygiene practices and clean techniques must be applied at all times.

Differences may be detectable during the study drug reconstitution, however active and placebo appear similar after reconstitution is complete (approximately 10 minutes). Throughout the study, a pharmacist (or other qualified personnel) will prepare study medication for injection, including confirmation of complete reconstitution, prior to delivery of study medication for injection. The pharmacist (or other qualified personnel) preparing study medication should not be involved with any study assessments and should not discuss any aspects of study drug reconstitution with the subject or study staff involved in subject interviews or study assessments to maintain the blind of the study.

The study drug does not contain preservatives. From a microbiological point of view, the preparation of the study drug has to be done as close to subject administration as possible, and the study drug should be used immediately (less than one hour) after reconstitution. If not used immediately, the study drug has to be used within four hours maximum after reconstitution stored at room temperature (below 30 °C) but only if the preparation has taken place applying strictly good hygiene practices and clean techniques to ensure controlled aseptic conditions.

12.1.4 Study Drug Injection

All study drug injections will occur at the study center, following instructions provided in the current versions of the pharmacy manual and Instruction for Use. After confirming that the study drug is fully reconstituted, the pharmacist (or other qualified personnel) will deliver the DCS to the investigator or other qualified personnel, for SC injection in the subject's abdomen or alternative injection site. A different injection site should be selected for each injection. Refer to the current versions of the Instructions for Use for further details. The site of injection should be recorded in the subject's treatment record as well as the eCRF at each time point.

For subjects willing and able to self-inject study medication and preferring to do self-inject, study center staff will provide training on study medication injections. Subjects will be allowed to inject medication at subsequent visits under supervision by study center clinic staff (with DCS preparation including reconstitution performed by the pharmacist or other qualified personnel and delivered for injection after reconstitution is complete). Study center/clinic staff can perform all injections if the subject is unwilling or unable to perform injections. The eCRF must record who performed study drug injection at each visit.

[figure not shown]
After study drug administration, subjects will be monitored closely for any signs or symptoms of hypersensitivity reaction before being discharged. For the first two visits where study drug is administered, subjects should remain at the study center for at least 30 minutes after study drug administration.

12.1.5 Packaging and Labeling

All IMP packaging and labeling operations will be performed according to Good Manufacturing Practice for Medicinal Products in the local language, national regulations/guidelines, and the relevant regulatory requirements, specifying that the drug is for use in a clinical study. Each DCS will be packaged in an individual carton, including a 27G ½" needle and a plunger rod (not assembled). Local adaptation of the kit design may be required; specific details for each country are provided in the pharmacy manual.

12.1.6 Study Drug Management

CCI

12.1.6.2 Dosing Schedule

Table 3 summarizes study drug dosing during the treatment period of the study.

Table 3 Treatment Period Dosing by Treatment Group

Group	Treatment	Dose at Day 1/Baseline	Dose at Week 4 and Week 8	Route	Schedule
1	30 mg Nemolizumab (CD14152)	60 mg (two 30 mg injections)	30 mg (30 mg injection + placebo injection)	SC	Q4W
2	60 mg Nemolizumab (CD14152)	60 mg (two 30 mg injections)	60 mg (two 30 mg injections)	SC	Q4W
3	Placebo	Placebo (two placebo injections)	Placebo (two placebo injections)	SC	Q4W

Abbreviation(s): Q4W = every four weeks; SC = subcutaneous.

12.2 Measures to Minimize Bias: Study Treatment Assignment

12.2.1 Allocation Concealment and Method of Study Treatment Assignment

Subjects will be centrally randomized using an Interactive Response Technology (IRT) system. Allocation concealment will be ensured, as the system will assign the randomization number only upon confirmation of eligibility for a given subject to participate in the study. Randomization will occur individually, the randomization number will be assigned to the unique Subject Identification Number (SIN) of each randomized subject, and the simultaneous randomization of groups of subjects will be prevented.

Subjects will be randomized in a 1:1:1 ratio to:

- Group 1: 30 mg nemolizumab Q4W with 60 mg loading dose at baseline;
- Group 2: 60 mg nemolizumab Q4W without loading dose at baseline; or
- Group 3: placebo Q4W.

Randomization will be stratified by clinical site.

[figure not shown]
12.2.2 Blinding

All attempts will be made to keep the study center staff and subjects blinded throughout the study. Members of the study center staff, including those responsible for DCS preparation, will not have access to the randomized treatment assignment.

To ensure double-blind administration of study drug, the study center pharmacist(s) or other qualified personnel will prepare all nemolizumab or placebo treatments, according to the current versions of the pharmacy manual and the Instructions for Use, of the assigned DCS provided by the IRT system.

As there may be detectable differences between active and placebo during the reconstitution process, the DCS is delivered for injection after the reconstitution is complete. The pharmacist (or other qualified personnel) preparing study medication should not be involved with any study assessments and should not discuss any aspects of study drug reconstitution with the subject or study staff involved in subject interviews or study assessments.

CCI

Unblinding of a subject's individual treatment code should occur only in case of a medical emergency or in the event of a serious medical condition that necessitates identification of the study drug for the welfare of that subject, as judged by the investigator. The emergency unblinding process utilizes IRT to allow the investigator to have unrestricted, immediate, and direct access to the subject's individual study treatment. When possible (i.e., when the health of the subject is not immediately at risk), the investigator or sub-investigator is encouraged to consult with the medical monitor and the sponsor before breaking the blind.

If emergency unblinding is required:

- Only the investigator will make the decision to unblind the treatment assignment.
- Only the affected subject will be unblinded.
- The IRT system will provide the treatment assignment to the investigator.

Refer to the IRT User Guide for information on the steps for breaking the blind.

When the blinding code is broken, the reason must be fully documented. If the code is broken by the investigator, the subject must be withdrawn from the study drug treatment and must also be appropriately followed for a minimum of 12 weeks after the last dose of study drug.

The reporting requirements for unblinding are the same for reporting an SAE. See also Section 16.12.2.

The randomization code will remain blinded to all study sites and study team members until completion of the study and after the study database has been locked.

The IDMC will review data at periodic intervals throughout the study as defined in the IDMC charter. The IDMC charter will specify the procedures for unblinding to ensure that treatment assignment remains undisclosed to all individuals involved in the direct execution and management of the study until the final database is locked.

12.3 Dosage Modifications

Dosage modification of the study drug will not be permitted during the clinical study. Any inadvertent dose modification(s) should be reported to the sponsor/CRO.

In the event of a missed dose (i.e., temporary discontinuation of the study drug), it will be documented in the eCRF that the drug has not been administered at the study visit, together with the reason (e.g., for safety). Subjects will be asked to return to the study centers for all remaining visits and complete all study assessments and procedures as described in Section 13.1.

Dosing frequency is scheduled for Q4W, based on the baseline/Day 1 visit date. If a study visit occurs outside the visit window (see Table 5), study drug can be administered provided there is a minimum of three weeks since the last injection. Future visits should be scheduled within the required windows based on the baseline/Day 1 visit date, while maintaining the minimum 3-week interval between two injections.

The rationale for the nemolizumab dose/dose regimen is provided in Section 8.6.

12.4 Treatment Accountability and Compliance

Study drug will be provided to the investigational site, and site personnel will acknowledge receipt of the study drug using IRT to confirm the shipment condition and content as per the current version of the pharmacy manual.

The designated personnel will also maintain accurate records of the study drug throughout the clinical study, including the inventory delivered to the study center, the use by each subject, the reconciliation of all delivered and received DCS units, and the return/destruction of unused study drug as specified in the current version of the pharmacy manual. No unauthorized use is permitted. Used DCS units will be properly documented in drug accountability records. Unless a product technical complaint (PTC) is detected or an event occurs before, during, or just after the injection, the used DCS can be disposed in an appropriate sharps container and according to waste regulation(s) in the country. A DCS involved in a malfunction or an investigator or subject complaint must be retained on site and designated personnel must proceed as defined in the current version of the pharmacy manual. Refer to Section 12.6 for PTCs.

The study monitor may check the study supplies at each study center at any time during the study. It is the responsibility of the study monitor to ensure that the investigator (or designee) has correctly documented the amount of the study drug received, dispensed, and returned/destroyed on the dispensing log that will be provided. A full drug accountability log will be maintained at the study center at all times. The study monitor will arrange collection of any unused study drug. The study monitor will also perform an inventory of study drug at the close-out visit to the study center. All discrepancies must be accounted for and documented appropriately in conjunction with the supply chain manager.

12.4.1 Dispensing and Return of Study Drug

All drug preparation must be appropriately performed and documented by the designated personnel. Any error in the preparation of the dose must be reported to the study monitor promptly and be properly documented. At the end of the study, the reconciliation/return/destruction process for all unused study drug will be conducted according to the pharmacy manual.

12.4.2 Compliance

Treatment compliance will be assessed through the treatment records.

As study drug is administered in the clinic, treatment compliance will be overseen and documented by the investigator and study staff (using the treatment records and drug accountability records). At a minimum, date, time, dose, injector (subject or site staff), and site of injection should be accurately recorded to confirm that each dose of study treatment was properly administered.

12.5 Prior and Concomitant Therapy

Prior therapies are defined as therapies that have been stopped within the three months before the screening visit, unless relevant to the inclusion/exclusion criteria. Whenever possible, all prior therapies for CKD-aP should be documented.

Concomitant therapies/medications are defined as follows:

- Any existing therapies ongoing at the time of the screening visit,
- Any changes to existing therapies (such as changes in dose, formulation or application frequency) during the course of the study, or
- Any new therapies received by the subject since the screening visit.

The following two categories are to be considered for prior and concomitant therapies:

- Drugs/Therapies include but are not limited to prescription, over-the-counter, birth control pills/patches/hormonal devices, vitamins, moisturizers, sunscreens, herbal medicines/supplements, vaccines (emergency or seasonal), and homeopathic preparations.
- Medical and surgical procedures (e.g., phototherapy, exodontia). Procedures whose sole purpose is diagnosis (non-therapeutic) are not included.

Prior and concomitant therapies for drugs/therapies or for medical/surgical procedures are to be recorded in the appropriate eCRF.

Concomitant therapies are to be recorded, reviewed, and updated at each visit.

At each visit, investigators should also confirm concomitant therapies for contraception. Contraceptive counseling should occur at screening.

Any new concomitant therapy or modification of an existing therapy may be linked to an AE. In such cases, a corresponding AE form should be completed to account for the new therapy or change in therapy, except in some cases such as dose modification for a chronic condition (see Section 12.3), in which case the medication will be linked to an item in the subject's medical history.

12.5.1 Permitted Concomitant Therapy

Unless specified as prohibited therapies (see Section 12.5.2), all therapies are authorized, including basic skin care (cleansing and bathing), moisturizers, bleach baths, stable antihistamines, and stable TCS.

The formation of cytochrome P450 (CYP450) metabolic enzymes can be altered by increased levels of certain cytokines (e.g., IL-1, IL-6, IL-10) during chronic inflammation. Although there is no known evidence suggesting that IL-31 affects the level or activity of CYP450 enzymes, the impact of nemolizumab on such enzymes has not been studied. Therefore, investigators should consider observing for clinical or laboratory signs that might indicate a potential effect of nemolizumab in subjects using concomitant therapies that are CYP450 substrates, particularly those with a narrow therapeutic index. Typical examples of substrates with a narrow therapeutic range include warfarin, drugs that may cause torsade de pointes, almost all cytotoxic antineoplastic drugs, and aminoglycoside antibiotics. A list of representative CYP450 substrates with narrow therapeutic index can be found in [Appendix 2](#).

12.5.1.1 *Moisturizer*

The subjects' current moisturizer or a moisturizer recommended by the investigator may be used. Whenever possible, subjects should use the same moisturizer throughout the study.

12.5.1.2 *Rescue Therapy*

If deemed to be medically necessary by the investigator (e.g. to control intolerable pruritus), rescue therapies can be prescribed to the subjects at any time during the study except during the screening period. Subjects receiving treatments defined as rescue therapies during the screening period are not eligible to participate in the study (see exclusion criterion 20 in Section 11.3).

As a general guideline and per individual investigator judgment, rescue therapy should not be prescribed within the first four weeks after baseline to allow a minimum time for study drug exposure in the presence of background therapy.

Investigator assessments of efficacy should be performed before initiating rescue therapy. Subjects requiring rescue therapy between scheduled visits should return to the clinic (unscheduled visit) for investigator assessment of efficacy before starting rescue therapy. The Investigator must contact the Medical Monitor prior to initiating rescue therapy.

As judged appropriate by the investigator, and following discussion with the Medical Monitor, rescue therapies are defined as below and include the following treatments:

- Antihistamines (new or increased dose): For those given as needed (“PRN”), at baseline, rescue of antihistamine is defined as that with an increase by $\geq 75\%$ in the total weekly dose relative to the dose during the last week of screening administered for ≥ 1 week.
- Gabapentin (new or increased dose) administered for ≥ 1 week.
- Selected Opioids: Nalbuphine or kappa opioid agonists (e.g., difelikefalin, nalfurafine), one or more doses
- Ultraviolet radiation therapy: one or more treatments

Note: all new concomitant medication or increase of frequency or increase of dose will be recorded.

Whenever possible, investigators should first use topical medications as rescue therapy before escalating to systemic therapies. If subjects receive topical treatments or phototherapy as rescue therapy, study drug administration should be continued unless there is a safety concern according to the investigator’s judgment. If subjects receive systemic rescue therapy, the study drug administration can be discontinued if the subject is at risk (discussed and agreed upon with investigator and medical monitor).

Further, the use of any rescue therapies should be documented in the eCRF.

12.5.2 *Prohibited and Restricted Medication/Therapy*

Treatment with the following concomitant medications/therapies is prohibited during the study unless otherwise specified in [Table 4](#). Pro re nata (PRN) use of TCS or TCI is not permitted.

Table 4 Prohibited and Restricted Medication/Therapy

Treatment(s)	Timeframe	
	Before Screening	Screening Period and Day 1 – Week 20
Systemic corticosteroids (i.e., administered by the intravenous, oral, or intramuscular route at a dose). Note: Low dose prednisone (up to 10 mg per day [or equivalent other corticosteroid]) is permitted if the dose has been stable for 2 weeks prior to Screening. Note: Use of steroids given by other routes (inhaled, topical for indications other than itching, ophthalmic, intra-articular, etc. are permitted).	Not allowed for 4 weeks, other than stable low dose prednisone or equivalent	Prohibited, other than stable low dose prednisone or equivalent
Topical corticosteroids	Not allowed for 2 weeks	Prohibited
Topical PDE-4 inhibitor	Not allowed for 2 weeks	Prohibited
TCIs	Not allowed for 2 weeks	Prohibited
Biologics and their biosimilars (e.g. etanercept, adalimumab, infliximab, omalizumab, etc.)	Not allowed for 8 weeks or 5 half-lives (whichever is longer)	Prohibited
Dupilumab	Not allowed for 10 weeks	Prohibited
Cannabinoids	Not allowed for 2 weeks	Prohibited
Immunosuppressive or immunomodulatory drugs (e.g. cyclosporine A, oral tacrolimus, cyclophosphamide, azathioprine, methotrexate, mycophenolate mofetil, JAK inhibitors)	Not allowed for 4 weeks or 5 half-lives (whichever is longer)	Prohibited
Systemic and topical antihistamines (excluding for ophthalmic use)	Stable dose for 2 weeks	Stable dose
Local anesthetics such as pramoxine, seed oil, capsaicin, topical ketamine, CBD oil, various lotions with anti-pruritic effects, etc.	Not allowed for 1 week	Prohibited
Gabapentin and pregabalin	Stable dose for 2 weeks	Stable dose
Phototherapy or tanning beds	Not allowed for 4 weeks	Prohibited
Selected Opioids Nalbuphine or kappa opioid agonists (e.g., difelikefalin, nalfurafine)	Not allowed for 4 weeks	Prohibited
All other opioids (e.g. codeine, tramadol, oxycodone, hydrocodone, methadone, buprenorphine)	Stable dose for 2 weeks	Stable dose

Treatment(s)	Timeframe	
	Before Screening	Screening Period and Day 1 – Week 20
Change in hemodialysis treatment (i.e., number of hemodialysis sessions per week, change in dialyzer or switch between hemodialysis and hemodiafiltration) Also see inclusion #2	Not allowed for 8 weeks	Prohibited
Live attenuated vaccine and non-live vaccine (Seasonal vaccine (e.g., influenza), emergency vaccine (e.g., rabies or tetanus) and COVID as noted in Section 12.5.2 are permitted)	Not allowed for 4 weeks	Prohibited

Note: Subjects should not interrupt ongoing treatment with medications important for the subject's health for the sole purpose of participating in this study.

Abbreviations: PDE-4 = phosphodiesterase-4; TCI = topical calcineurin inhibitor; TCS = topical corticosteroid.

For medications given as needed (“PRN”), stable dose during the study is defined as that without an increase or decrease by $\geq 75\%$ in the total weekly dose relative to the dose during the last week of screening. For example, if the total weekly dose of 100 mg of diphenhydramine during the last week of the Screening Period increased to 175 mg in a given week during the study, this would be considered not a stable dose. During the Screening Period, a “stable dose” is one that has not changed (increase or decrease) by $\geq 75\%$ during the period of required stability.

Note: Subjects should not interrupt ongoing treatment with medications important for the subject's health for the sole purpose of participating in this study.

If a prohibited therapy becomes necessary for the safety of the subject, the investigator should notify the medical monitor and discuss possible alternatives. If a subject receives a prohibited therapy during the clinical study (e.g., inadvertent short-term use), the investigator should also notify the medical monitor and discuss whether or not it is acceptable for the subject to continue receiving the study drug.

If the use of systemic corticosteroids more than prednisone 10 mg per day or equivalent becomes necessary for the safety of the subject to treat conditions other than CKD-aP, the study drug should be temporarily discontinued for the duration of treatment with systemic corticosteroids plus five half-lives.

It is recommended that all subjects should be up to date with respect to standard of care vaccinations as defined by the local guidance. For subjects who have vaccination planned during the study, other than allowed vaccinations below, it will be determined after consultation with the treating physician, whether the administration of vaccine can be postponed until after the end of study, or preponed to before the start of the study, without compromising the health of the subject.

Vaccinations during the study including the screening and follow-up periods are not permitted, except for use of the following non-live vaccines:

- Seasonal vaccinations (e.g., influenza)
- Emergency vaccinations (e.g., rabies or tetanus)
- COVID-19 vaccinations

Wherever possible, it is recommended to avoid administration of seasonal and COVID-19 vaccinations +/- one week from study drug dosing. A different anatomical location should be used for study drug administration and vaccine administration.

In the event of emergency vaccination (e.g., rabies or tetanus) during the study, the study drug administration should be discontinued until the immune response to vaccination is verified. It is recommended to discuss with the medical monitor before discontinuing the study drug.

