4.11.4 Safety Set

The Safety Set includes all randomized subjects who receive at least one dose of study drug. All safety data will be summarized based on the Safety Set. Subjects will be summarized according to their actual treatment group.

CC1

5 Estimands

The estimands for primary and key secondary endpoints provide precise descriptions of the treatment effect reflecting the clinical questions posed by the trial objectives. They summarize at a population level what the outcomes would be in the same patients under different treatment conditions being compared.

The intercurrent events are events occurring after treatment initiation that affect either the interpretation or the existence of the measurements associated with the clinical question of interest. It is necessary to address intercurrent events when describing the clinical question of interest in order to precisely define the treatment effect that is to be estimated.

The intercurrent events identified for this study and the estimands for primary and key secondary endpoints are defined in the following tables.

Table 5 List of Intercurrent Events

Intercurrent Event	Strategy to Deal With Intercurrent Event Within Analysis	Assessment of Subjects
Rescue therapy	Composite strategy	Subjects will be considered as treatment failures. The values of the variable of

Intercurrent Event	Strategy to Deal With Intercurrent Event Within Analysis	Assessment of Subjects
		interest collected after the use of rescue therapies will be set to the worst possible value and subject's binary response will be imputed as "Non-responder"
Treatment discontinuation due to lack of efficacy or AE/death related to study drug	Composite strategy	Subjects will be considered as treatment failures. The values of the variable of interest collected after treatment discontinuation due to lack of efficacy or AE/death related to study drug will be set to the worst possible value and subject's binary response will be imputed as "Non-responder"
Treatment discontinuation due to any other reason	Treatment-policy strategy	The values of the variable of interest are used regardless of the occurrence of treatment discontinuation

Table 6 Estimand of Primary Efficacy Endpoint

Primary Efficacy Estimand Description	Estimand Attributes

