8.3 Rescue Therapies

Rescue therapies are defined as below and include the following treatments:

- Antihistamines (new or increased dose): For those given as needed (“PRN”), at baseline, rescue of antihistamine is defined as that with an increase by $\geq 75\%$ in the total weekly dose relative to the dose during the last week of screening administered for ≥ 1 week.
- Gabapentin (new or increased dose) administered for ≥ 1 week.
- Selected Opioids: Nalbuphine or kappa opioid agonists (e.g., difelikefalin, nalfurafine), one or more doses.
- Ultraviolet radiation therapy: one or more treatments.

For the purpose of efficacy analyses (including sensitivity and supplementary analyses), that are not based on Observed Case (OC), subjects receiving any rescue therapies will be considered as treatment failures. Efficacy data collected after the use of rescue therapies will be set to the worst possible value for continuous variables and subject’s binary response will be imputed as “Non-responder” prior to conducting the MI and Tipping Point analysis.

Investigator assessments of efficacy should be performed before initiating rescue therapy. Subjects requiring rescue therapy between scheduled visits should return to the clinic (unscheduled visit) for investigator assessment of efficacy before starting rescue therapy.

Rescue medications will be summarized for the ITT Set, by rescue therapy type (topical, systemic) and, within each rescue type, by ATC class level 2, ATC class level 4 and preferred term overall and for each therapy. ATC class level 2 and ATC class level 4 will be sorted in decreasing order of frequency based on the total number of subjects of all treatment groups and within each drug class, preferred terms will be presented in decreasing order of frequency.

Rescue procedures will be summarized for the ITT Set, by rescue therapy type (phototherapy) and by SOC and PT overall and for each therapy. SOC will be sorted in decreasing order of frequency based on the total number of subjects of all treatment groups and within each SOC, PT will be presented in decreasing order of frequency.

Rescue therapies data including specific details will be presented in a listing.

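### The rescue list behind the composite endpoints names gabapentin but not pregabalin, and leaves unclear whether a topical recorded as rescue counts

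*Protocol*

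**What the plan says.** Protocol 12.5.1.2 (repeated in the synopsis and in 10.2) and SAP 8.3 list the same four rescue classes: antihistamines, gabapentin, nalbuphine or kappa opioid agonists, and ultraviolet therapy. The gabapentin entry reads "Gabapentin (new or increased dose) administered for" at least one week. Pregabalin is not listed. In protocol Table 4 one row covers "Gabapentin and pregabalin" and requires a stable dose of either drug through Week 20.

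On topicals, protocol 12.5.1.2 says: "Whenever possible, investigators should first use topical medications as rescue therapy before escalating to systemic therapies". It adds: "If subjects receive topical treatments or phototherapy as rescue therapy, study drug administration should be continued", subject to safety. SAP 8.3 states that "subjects receiving any rescue therapies will be considered as treatment failures" in every efficacy analysis not based on observed cases, and it plans to summarise rescue medication "by rescue therapy type (topical, systemic").

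SAP Section 5 ("Table 5 List of Intercurrent Events") has three events. Rescue therapy, and discontinuation for lack of efficacy or a drug-related adverse event or death, follow a composite strategy. Discontinuation for any other reason follows treatment policy. No event covers other anti-itch therapy.

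**The concern.** A composite endpoint should classify like cases alike. Here two closely related drugs that the protocol restricts on identical terms lead to opposite outcomes when started for itch by a subject who stays on study drug. The topical instruction raises a second question. Investigators are steered to topicals as the first step of rescue, yet the list that decides failure barely mentions them. If the programmer and the blinded reviewers have to decide what counts, a component of the primary endpoint rests on interpretation.

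At stake is the responder status of a few subjects in Estimands 1 to 6. The Week 12 estimands (1, 2 and 4) are the most exposed, because rescue is discouraged in the first four weeks.

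**Working it through.** **Step 1: trace four subjects through the rules.** Each improves by at least 4 points at Week 12 and stays on study drug.

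| Therapy for itch | On the four-class list? | Caught by the discontinuation event? | Status |
|---|---|---|---|
| Gabapentin, new, 1 week | Yes | Not needed | Non-responder |
| Pregabalin, new, 1 week | No | No | Responder can result |
| Topical recorded as rescue | Only if an antihistamine | No; study drug should continue | Unclear |
| Prohibited topical, not recorded as rescue | No | No | Responder can result |

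Stopping study drug would not close the pregabalin gap either. Unless the stop is coded as lack of efficacy or a drug-related event, treatment policy applies and observed values are used.

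Restriction does not explain the omission. Kappa agonists and phototherapy are prohibited in Table 4, and gabapentin is held to a stable dose, yet all three count as rescue.

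**Step 2: reproduce the planned power.** Inputs (protocol 19.1, SAP 4.2): 84 per arm, 20% versus 50%, two-sided 0.025.
- Null standard error: √(2 × 0.35 × 0.65 / 84) = 0.0736.
- Alternative standard error: √((0.20 × 0.80 + 0.50 × 0.50) / 84) = 0.0699.
- Power: Φ((0.30 − 2.241 × 0.0736) / 0.0699) = 97.3%.

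Exact binomial enumeration with a single-stratum CMH statistic, counting rejections that favour active, gives 97.4%. Both agree with the stated figure of at least 90%. The false-positive rate in favour of active at 20% versus 20% is 1.2%.

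**Step 3: size under assumed rates.** The documents give no use rate. Assume that 2% to 10% of an arm use any unlisted anti-itch therapy and that 10% to 25% of those users then meet the criterion. Pregabalin would be only part of this. The shift is use × conversion:
- low: 0.02 × 0.10 = 0.2 points (0.2 of 84 subjects);
- middle: 0.05 × 0.25 = 1.25 points;
- high: 0.10 × 0.25 = 2.5 points (2.1 of 84);
- stress: 0.10 × 0.50 = 5.0 points (4.2 of 84).

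| Shift (points) | Power, both arms | Power, placebo only | False positive, active only, true 20% v 20% |
|---|---|---|---|
| 0 | 97.4% | 97.4% | 1.2% |
| 1.25 | 97.1% | 95.8% | 2.0% |
| 2.5 | 96.8% | 93.7% | 3.2% |
| 5.0 (stress) | 96.3% | 87.3% | 7.1% |

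A 2.5-point shift in both arms at true 20% versus 20% leaves the false-positive rate at 1.2%.

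**Step 4: effect on a result at the planned rates.** With a active responders, m responders in total and N = 168, the CMH statistic is (a − m/2)² / [m(N − m) / (4(N − 1))]. For 42 versus 17 it is 12.5² / (59 × 109 / 668) = 16.2, p = 0.00006. Removing 2 active responders (40 versus 17) gives p = 0.0002; removing 4 (38 versus 17) gives p = 0.0006.

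These figures ignore stratification by analysis center and multiple imputation.

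**The case against.** The strongest reply concerns topicals. A reader might infer that topical rescue escapes the endpoint. The documents do not show that. The lead-in to the list both defines and includes, so it can be read as non-exhaustive. All rescue is to be documented in the eCRF. SAP 8.3 fails subjects on any rescue and plans a topical category. The antihistamine entry sets no route, and Table 4 covers topical antihistamines. Most other antipruritic topicals are prohibited, and the Medical Monitor must be contacted before rescue begins. On that reading a topical recorded as rescue is already a failure. This stands: the topical part is an ambiguity, not a demonstrated error.

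On pregabalin, a shared row in Table 4 does not make a drug rescue. Other opioids are also held to a stable dose and are not rescue. Protocol Section 11 names antihistamines and gabapentin as the commonest prescriptions in this condition, which plausibly explains why gabapentin was listed. A new or increased pregabalin dose also breaches the stable-dose rule. This limits frequency, but it does not classify the subject.

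Several planned outputs give partial checks:
- Supplementary Analysis 3 ignores rescue and discontinuation, so it treats gabapentin and pregabalin alike. It uses observed cases and fails no one.
- The per-protocol analysis can exclude users of prohibited therapy. It covers the primary endpoint only, is decided case by case, and drops subjects rather than failing them.
- Major deviations and concomitant medications are tabulated by arm, so an imbalance would be visible.
- The systemic anti-pruritus subgroup mixes prior and stable users with new starters.

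Sensitivity Analyses 1 to 6 do not help, because all keep the same rescue definition.

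**Conclusion.** The pregabalin omission is real: a stated rule classifies like cases differently in Estimands 1 to 6. The status of a topical recorded as rescue is ambiguous and should be settled in writing. The point is minor.

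The size cannot be known from the documents and is probably small. Across the assumed range, power at the planned rates stays at 93.7% or more, and a result at those rates is not threatened. Heavier use on placebo would be conservative, and equal use leaves the false-positive rate essentially unchanged.

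Two further inferences are not supported. One is that the gap biases the trial towards nemolizumab. That needs use concentrated in the active arm, and nothing in the documents suggests it. The other is that every prohibited therapy started for itch must become a composite failure. That is a debatable estimand choice; leaving such use to observed values, with the per-protocol analysis as a check, is defensible. Table 4 does separate steroids given as "topical for indications other than itching", but the documents do not say whether the eCRF records the indication for every therapy.

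**What to change.** Before unblinding:

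(a) Add pregabalin to the rescue list (protocol 12.5.1.2 and its repeats in the synopsis and 10.2; SAP 8.3), new or increased for at least one week, on the same terms as gabapentin.

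(b) State in SAP 8.3 and Table 5 that any therapy the investigator records as rescue in the eCRF counts as rescue, topicals included.

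For unlisted prohibited anti-itch therapy that was not recorded as rescue, leave the primary composite as it is. Add a supplementary analysis that counts those users as non-responders, with cases identified at the blinded data review already planned in SAP 6.2. If the indication is missing, query the sites while still blinded.

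The cost is a wording amendment, a medication check at an existing meeting, and perhaps a few more non-responders. All new or increased medications are already recorded. Because (a) changes a component of the primary endpoint, SAP Section 16 probably calls for a protocol amendment and not only a SAP update; if it is classed as substantial, protocol 20.7.1 requires regulatory and ethics approval.
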